9.3.2 Exposure

- **Pregnancy delivery date** is the date on which delivery occurred.
- The **days postpartum** will be calculated as the difference between the date of the most recent delivery and the IUD insertion date and will be expressed in days. Data for days postpartum will not be captured for women with no evidence of delivery in the past year (52 weeks).
- **Postpartum status** will consist of three variables: two dichotomous variables and a four-level categorical variable. In all of these variables, women with no evidence of delivery in the past year (52 weeks) will be classified as “no delivery in the past 52 weeks.”
 - **Postpartum status categories for primary objective** will consist of the following four categories (as proposed by the FDA).
 - ≤ 6 weeks postpartum
 - > 6 weeks and ≤ 14 weeks postpartum
 - > 14 weeks and ≤ 52 weeks postpartum
 - > 52 weeks postpartum (including women without recorded delivery in the past 52 weeks)
 - **Postpartum status at IUD insertion for sensitivity analysis** will be a dichotomous comparison of ≤ 14 weeks postpartum versus > 14 weeks postpartum (including women with no evidence of delivery in the past year [52 weeks]).
 - **Postpartum status similar to EURAS-IUD** will be a dichotomous comparison of IUD insertions occurring ≤ 36 weeks postpartum versus > 36 weeks postpartum (including women with no evidence of delivery in the past year [52 weeks]).
- **Breastfeeding status** at the time of IUD insertion: any evidence of breastfeeding (i.e., any breastfeeding or pumping across a 24-hour period) at the time of IUD insertion will be determined based on linked mother/infant records (e.g., well-child visits, infant check-ups, and immunization visits) and clinical notes for the woman and infant. Breastfeeding status will be classified as yes (last breastfeeding date within 14 days before IUD insertion or after IUD insertion), no (last breastfeeding date more than 14 days before IUD insertion; first non-breastfeeding date before IUD insertion), or undetermined. Breastfeeding status will not be ascertained for women with no evidence of a live birth in the past year (52 weeks) and those women will be classified as not breastfeeding.

- **IUD type:** three-level categorical variable of inserted IUD type:
 - LNG-IUD: Mirena, Liletta, Skyla, Kyleena
 - Copper IUD: ParaGard, other copper
 - Unknown IUD type
- **Menorrhagia: diagnosis of menorrhagia will be assessed in two variables**

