- **Continuous enrollment**, in days, that each individual is in the data source will be calculated starting on the earliest date of date of enrollment in database or date of first clinical encounter in database and ending on the earliest of date of disenrollment from database, date of last clinical encounter in database, or end date of study period, allowing up to one 31-day gap in enrollment each year to be considered continuously enrolled. The individual's start and end dates in the enrollment files will be used for KPNC, KPSC, and KPWA. For RI, the start date will be designated as the patient's first clinical encounter within the dataset, and the end date will be the patient's last observation within the dataset. There may be multiple continuous enrollment periods for a woman who moves out of then back into the database.
- **Live birth at most recent delivery:** indicator variable (0 = No, 1 = Yes) for whether the patient had pregnancy ending in live birth within the past 52 weeks.

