9.4.3 Kaiser Permanente Washington

Based in Washington state, KPWA (formerly Group Health Cooperative) is a nonprofit health system that currently serves over 650,000 members and provides primary, specialty, home health, and inpatient skilled nursing care. Members reside in 22 counties in Washington and northern Idaho. Approximately 70% of patients receive comprehensive care in KPWA-owned facilities, including 25 primary care medical centers and six specialty medical centers. The remaining 30% receive care from contracted provider networks in geographic areas not served by KPWA medical centers but reimbursed by KPWA.

The EHR system was fully implemented in 2006 and includes datasets on enrollment, encounters, diagnoses, procedures, vital signs, radiology, pathology, laboratory tests, and pharmacy dispensings. Data are linked across all databases via a unique member identifier. The mother-infant database (used to collect breastfeeding data) includes data on women with live births and linked infant records and is currently up to date through 2015.

In the validation study, continuous enrollment in KPWA was measured via enrollment files. Of all IUD insertions in this data source, 64% (more than 15,000) were in women with at least 12 months of continuous enrollment before the date of insertion.

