9.7.2.1 Study cohorts defined by exposure variables

Only women with eligible IUD insertions and nonmissing exposures will be included in analyses reliant on exposure status. Three cohorts of interest are defined based on need for nonmissing data:

- **Complete study population:** all first IUD insertions included in the data* based on study inclusion and exclusion criteria outlined in Section 9.2.2. This study cohort will include women with missing data for breastfeeding status, and/or IUD type.† The missing data within breastfeeding status and IUD type may be considered a separate group within the analyses.
- **Breastfeeding status:** all IUD insertions among women who were less than 52 weeks postpartum at the time of IUD insertion and had either “yes” or “no” breastfeeding status at the

* Objectives 18 and 23 are the only objectives that assess all IUD insertions. All other objectives assess only the first IUD insertion within the data for each woman.

† No missing data are anticipated for postpartum/no delivery status or menorrhagia. For both of these variables, lack of documentation associated with the variable would default the status for that IUD insertion to the unexposed or referent category of the variable.

time of IUD insertion will be included in this cohort. IUD insertions among women who have undetermined breastfeeding status will not be included.

- **IUD type:** all IUD insertions with a known type of IUD (either LNG-IUD or copper IUD) will be included in this cohort. IUD insertions among women who had an undetermined IUD type will not be included.

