3.1 Exposures

- *Pregnancy delivery date* is the date on which delivery occurred
- *Breastfeeding status* at the time of IUD insertion: breastfeeding status is defined for every insertion based on whether there is any evidence of breastfeeding (including any breastfeeding or pumping across a 24 hour period) at the time of IUD insertion. For postpartum \leq 52 weeks, breastfeeding status is defined as Yes, No, or Undetermined. For postpartum $>$ 52 weeks, including no evidence of a live birth in the past 52 weeks, breastfeeding is not assessed (and will be classified as No when used as a covariate).
- *IUD type*: three-level categorical variable indicating the type of IUD inserted:
 - LNG-IUD: Mirena, Liletta, Skyla, Kyleena
 - Copper IUD: ParaGard, other copper
 - Unknown IUD type

- *Menorrhagia*: diagnosis of menorrhagia assessed in two variables
 - As an exposure: indicator variable (0 = No, 1 = Yes) for whether the patient was diagnosed with menorrhagia in the year (365 days) prior to or on the index date
 - As a covariate within other exposure assessments: four-level categorical variable for whether the patient was diagnosed with menorrhagia
 - Diagnosed in the year prior to or on the index date, but not diagnosed before that time
 - Not diagnosed in the year prior to or on the index date, but was diagnosed before that time
 - Diagnosis recorded within the year prior to or on the index date and also before that time
 - No diagnosis of menorrhagia within the data

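### Protocol and SAP disagree on whether recently delivered women without live-birth evidence belong in the not-breastfeeding referent of primary objective 1

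*Protocol*

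**What the plan says.** **Protocol.** Section 9.3.2 measures time postpartum from the most recent delivery. Its breastfeeding rule depends on live birth instead: status is not ascertained for "women with no evidence of a live birth in the past year (52 weeks) and those women will be classified as not breastfeeding". The objective 1 cohort in 9.7.2.1 is "all IUD insertions among women who were less than 52 weeks postpartum at the time of IUD insertion and had either" a yes or a no. The only status it removes is the unresolved one: "IUD insertions among women who have undetermined breastfeeding status will not be included". Live birth is not a condition of entry, although 9.3.4 collects an indicator for "whether the patient had pregnancy ending in live birth within the past 52 weeks".

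**SAP.** Section 3.1 groups these women with those more than 52 weeks postpartum: "including no evidence of a live birth in the past 52 weeks, breastfeeding is not assessed". It limits the default, which "will be classified as No when used as a covariate". The same section also says that status is defined for every insertion, and that within 52 weeks it is Yes, No or Undetermined. Section 5.1.2 defines Analysis Set 2 by time postpartum and a yes or no status. Table 2 in section 5.1 splits its rows by delivery. Neither mentions live birth.

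**Related rules.** SAP 4.3 reads absent information on a binary variable as absence of the factor. Protocol 9.4.3 says that the KPWA mother-infant database "includes data on women with live births and linked infant records and is currently up to date through 2015", while insertions are eligible to about 30 April 2018 (Protocol 9.2.2).

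**The concern.** Delivery decides who is in the cohort, and live birth decides whether feeding status is looked up. A woman with a recorded delivery and no live-birth evidence falls between the two. Under the protocol she is a No by default and a referent. Under SAP 3.1 she has no assessed exposure, yet she also meets that section's rule for women within 52 weeks. Two programmers could build different Analysis Sets 2 for a primary objective.

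Such women are of two kinds:
- **Stillbirths.** No is factually correct. The question is whether women who could not have been breastfeeding are a suitable comparator.
- **Live births whose outcome was not captured.** No is a guess. If some of them breastfeed, exposed women sit in the referent and the hazard ratio moves toward 1. That is the unfavourable direction in a safety study that declines multiplicity adjustment so as not to miss a risk (Protocol 9.9).

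The default also reaches the adjustment. SAP 4.1.5 puts breastfeeding status into the propensity models in which it is not the dependent variable, so these women are coded No there, although SAP 5.1.1 allows missing breastfeeding status to be its own group.

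**Working it through.** **Inputs.** Protocol 9.5 and Table 4: 60,000 women with status, split 60:40 (36,000 breastfeeding, 24,000 referents); perforation risk 1.3 per 1,000; two-sided alpha 0.05. The number of delivered women without live-birth evidence is not given, so the shares below are assumptions.

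**1. The plan's own figure.** Events d = 60,000 × 0.0013 = 78. Schoenfeld power = Φ(√(d × p(1−p)) × ln HR − 1.96), with p = 0.6. At HR 2.0: √(78 × 0.24) = 4.327; 4.327 × 0.693 − 1.96 = 1.04; power 85.1%, against 85% stated. HR 1.5, 1.75, 2.25 and 2.5 give 41.9%, 67.8%, 93.9% and 97.8%, against 42, 68, 94 and 98 in Table 4. All are reproduced.

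**2. Dilution.** If a fraction f of the referent truly breastfeeds, the referent hazard is 1 + f(HR − 1) times the true unexposed hazard, so observed HR = HR / (1 + f(HR − 1)). With true HR 2.0 and events held at 78:

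| f | Women misclassified (f × 24,000) | Observed HR | Power |
|---|---|---|---|
| 1% | 240 | 1.98 | 84.0% |
| 2% | 480 | 1.96 | 83.0% |
| 5% | 1,200 | 1.90 | 79.6% |
| 10% | 2,400 | 1.82 | 73.5% |

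For scale, suppose that every defaulted woman had a live birth and 60% of them breastfeed. Then f = 2%, 5% and 10% need 480/0.6 = 800, 1,200/0.6 = 2,000 and 2,400/0.6 = 4,000 defaulted women, or 1.3%, 3.3% and 6.7% of the 60,000. Documented stillbirths contribute nothing to f.

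**3. KPWA worst case.** Assume that the file is never updated, that it is the site's only live-birth evidence, that deliveries are still recorded, that accrual is uniform, and that 60% breastfeed. The counts with 12 months of history in Protocol 9.4.1 to 9.4.4 (some given as lower bounds) sum to 100,000 + 80,000 + 15,000 + 5,700 = 200,700, so the KPWA share is 15,000/200,700 = 7.5%. January 2016 to April 2018 is 28 of the 148 months from January 2006.
- Women affected: 60,000 × (15,000/200,700) × (28/148) ≈ 848
- Breastfeeding among them: 0.6 × 848 ≈ 509
- f = 509/(24,000 + 509) = 2.1%
- Pooled HR: 2/1.021 = 1.96
- Power, with exposed share (36,000 − 509)/60,000: 83.1%

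**4. Cost of excluding them.** Removing 1%, 2%, 5% or 10% of the 24,000 referents leaves 59,760, 59,520, 58,800 or 57,600 women. Power at HR 2.0 is 84.8%, 84.6%, 84.0% or 82.7%. The largest loss is 85.1 − 82.7 = 2.4 points.

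**The case against.** The strongest reply is that the SAP already deals with this. It is the later document, it calls breastfeeding not assessed in these women, and it confines No to covariate use. In objective 1 breastfeeding is the exposure, and a status that was not assessed is neither yes nor no, so Analysis Set 2 would leave these women out. That is a fair reading of SAP 3.1. It does not close the matter. SAP 1.2 presents the plan as aligned with protocol version 2.0, the change list in SAP section 7 records no override of the protocol rule, and Table 2 has no cell for a delivered woman who was not assessed.

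A reader might infer more: that missing mother-infant linkage turns breastfeeding women into controls. The documents do not say that. The live-birth indicator describes the woman's pregnancy outcome and is not defined by infant linkage. Feeding status also comes from her own clinical notes. A known live birth without usable feeding data can be classed as undetermined, and that class is excluded. The plan's figures allow for such losses: 30% of 225,000 is 67,500 women within 52 weeks, against about 60,000 with status. SAP 4.3 makes the route from missing record to No conceivable, not demonstrated.

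Nor does the KPWA sentence show that the site loses its breastfeeding data after 2015. It describes the file when the protocol was written, and Table 3 gives KPWA a data end date of about 30 June 2018. A reader might also expect false differences between sites. In the worst case above, KPWA has 60,000 × 7.5% ≈ 4,484 women, and its own HR would fall to about 1.64 (509 among 1,794 + 509 referents is 22.1%; 2/1.221). But the site expects only 4,484 × 0.0013 ≈ 6 perforations, too few to tell 1.64 from 2.0.

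**Conclusion.** The point holds as an unresolved inconsistency on a primary exposure. The protocol states a default to No that admits women of unascertained status to the objective 1 referent. SAP 3.1 leans against it, and the SAP's analysis-set definitions leave it open.

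Any bias is toward a hazard ratio of 1. Its size rests on a count that the documents do not give: a true 2.0 becomes 1.96 to 1.82 if an assumed 2% to 10% of the referent truly breastfeeds, and the KPWA worst case moves the pooled ratio only to about 1.96. These figures assume constant hazards within feeding groups and uncaptured live births among the defaulted women. If all of those women had stillbirths there is no misclassification, and what remains is comparability. The power figures in Table 4 are correct on their stated inputs. The change is worth making because it is cheap and settles who is in the primary comparison, not because a large bias has been shown.

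**What to change.** Reconcile protocol 9.3.2 and 9.7.2.1 with SAP 3.1, 5.1.2 and Table 2:

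- Define Analysis Set 2 as delivery within 52 weeks, and live birth at most recent delivery = 1, and breastfeeding status yes or no.
- Code delivered women with unknown birth outcome as Undetermined, including where breastfeeding is a propensity-score covariate.
- Keep the default No only for women with no delivery in the past 52 weeks.
- Report by site the number of delivered women without live-birth evidence. This would also show whether KPWA after 2015 stands out.

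**Cost.** A few lines of text, since the live-birth indicator is already collected (Protocol 9.3.4, SAP 3.8). As defined it is 0/1, which is enough for Analysis Set 2. Separating documented stillbirths from unknown outcomes, for the covariate coding, needs a third level from the sites. There will be slightly fewer non-breastfeeding referents, with a loss of at most about 2.4 points of power if 1–10% of them are removed.

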9.3.3 Outcome measures

- **Person-time at risk** will be calculated from the IUD insertion date until the first occurrence of any of the following: uterine perforation, IUD expulsion, or censoring date.
- **Date uterine perforation confirmed** is the date on which uterine perforation is documented. This may be complete perforation, with IUD migration into the pelvis or abdominal cavity, or partial perforation (i.e., incomplete, with IUD embedded in the myometrium). Cases of both partial and complete perforation will be considered under the umbrella term “perforation.” Cases will be classified as yes, no, or undetermined perforation.
- **Date IUD expulsion confirmed** is the date on which IUD expulsion is documented. IUD expulsion, which is the unintended, spontaneous expulsion of the IUD, will be determined from the EHR, including clinical notes, using algorithms developed during the validation study. Both partial and complete expulsions will be considered under the umbrella term “expulsion.” Cases will be classified as yes, no, or undetermined expulsion.

If both perforation and expulsion (e.g., complete or partial perforation of the *vagina or cervix* by the IUD) occurred and were documented on the same date, then the outcome will be classified as both perforation and IUD expulsion, since these outcomes are evaluated separately throughout this study. If both perforation and IUD expulsion occurred for the same IUD insertion but on different dates, then the earlier date will constitute a stopping date for assessment of all objectives. No analysis will be conducted to assess both perforation and IUD expulsion as a composite outcome or as a subgroup analysis among those with both outcomes.

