3.2 Outcomes

- *Date uterine perforation confirmed* is the date on which uterine perforation is documented. Either partial or complete perforation will be considered as an outcome, and no distinction will be made between partial and complete perforation.
- *Date IUD expulsion confirmed* is the date on which IUD expulsion is documented. Either partial or complete expulsion will be considered as an outcome, and no distinction will be made between partial and complete expulsion.

If both perforation and expulsion occurred on the same date, then the outcome will be classified as both perforation and expulsion, since these outcomes are evaluated separately throughout this study. No analysis will be conducted to assess both perforation and IUD expulsion as a composite outcome or as a subgroup analysis among those with both outcomes.

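### Protocol 9.3.3 describes uterine perforation by pelvic, abdominal or myometrial location, yet its same-date rule counts a vaginal or cervical perforation as both outcomes, so expulsion-related cases can enter the primary endpoint unseen

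*Protocol*

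**What the plan says.** Protocol 9.3.3 (Outcome measures) describes the event as "complete perforation, with IUD migration into the pelvis or abdominal cavity, or partial perforation (i.e., incomplete, with IUD embedded in the myometrium"). The vagina and cervix are not listed.

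After the outcome bullets, the same section deals with women who have both outcomes, and puts its illustration in brackets: "If both perforation and expulsion (e.g., complete or partial perforation of the *vagina or cervix* by the IUD) occurred and were documented on the same" (day). For such a case the rule is "then the outcome will be classified as both perforation and IUD expulsion, since these outcomes are evaluated separately throughout this study".

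SAP 3.2 carries the rule over without the illustration: "If both perforation and expulsion occurred on the same date, then the outcome will be classified as both perforation and expulsion". On what qualifies as perforation it says only "Either partial or complete perforation will be considered as an outcome, and no distinction will be made between partial and complete perforation", with no anatomical site. SAP Table 1 sets each event indicator from its own confirmation date, so a same-date case is an event in both models. SAP 6.2 makes time to diagnosis of uterine perforation the primary endpoint.

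Both Protocol 9.3.3 and SAP 3.2 add, on women with the two outcomes: "No analysis will be conducted to assess both perforation and IUD expulsion as a composite outcome or as a subgroup analysis among those with both".

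**The concern.** A case that meets only the illustration (device through the vagina or cervix) does not match the sites named in the description just above it. Followed literally, the rule still scores it as a uterine perforation.

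The study treats perforation and expulsion as separate outcomes and asks of each whether it depends on breastfeeding and postpartum timing (objectives 1 and 2; 20 to 23). A class of cases shared by both endpoints is a channel through which an effect on expulsion alone could appear in the perforation test. That test is run at a two-sided 0.05 level without multiplicity adjustment.

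No planned output would show whether this happened. The only sensitivity analysis for the primary objectives replaces weighting by covariate adjustment (SAP 6.2.1). Table Layout 1 puts the two outcomes in separate columns without a cross-count. Events are also few: at the planning risk, the ≤ 6 weeks group expects 11,250 × 0.0013 = 14.6 perforations, so a handful of cases could move that estimate.

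**Working it through.** **Step 1. Reproduce the plan's power base.** Inputs from Protocol 9.5 and Table 4: risk 1.3 per 1,000; two-sided α = 0.05; objective 1 has N = 60,000 at 60:40; ≤ 6 weeks has N = 168,750 at 5:70; > 6 to ≤ 14 weeks has N = 202,500 at 20:70.

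With D = N × 0.0013 events, p the exposed share and d = √(D·p·(1−p)) × |ln HR|, the two-sided Schoenfeld rejection probability is Φ(d − 1.96) + Φ(−d − 1.96).

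| Comparison | D | p | √(D·p·(1−p)) | Power at HR 2.0 | Table 4 |
|---|---|---|---|---|---|
| Breastfeeding | 78.0 | 0.60 | 4.33 | 85.1% | 85% |
| ≤ 6 weeks | 219.4 | 5/75 | 3.69 | 72.6% | 73% |
| > 6 to ≤ 14 weeks | 263.2 | 20/90 | 6.75 | 99.7% | > 99% |

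The other cells of Table 4 also reproduce. The power figures are not in dispute; they only supply event numbers for the next steps.

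**Step 2. Mixture of event types.** Let q be the share of referent-group perforation events that are vaginal or cervical only. Let HR_P be the hazard ratio for true perforation and HR_E the one for these cases. If the referent hazard is h, the exposed hazard is (1−q)·h·HR_P + q·h·HR_E, so

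observed HR = (1−q)·HR_P + q·HR_E.

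**Step 3. Assumed range.** The documents give neither q nor HR_E. Take HR_P = 1, q from 2% to 20% and HR_E from 2 to 4, and put the observed HR into the formula of Step 1.

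| q | HR_E | Observed HR | Reject, ≤ 6 weeks | Reject, > 6 to ≤ 14 weeks |
|---|---|---|---|---|
| 2% | 2 | 1.02 | 5.1% | 5.2% |
| 5% | 2 | 1.05 | 5.4% | 6.2% |
| 5% | 3 to 4 | 1.10 to 1.15 | 6.4% to 8.1% | 9.9% to 15.6% |
| 10% | 3 to 4 | 1.20 to 1.30 | 10.3% to 16.3% | 23.3% to 42.5% |
| 20% | 3 to 4 | 1.40 to 1.60 | 23.7% to 41.2% | 62.2% to 88.7% |

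Worked cell: q = 10%, HR_E = 3 gives 0.9 + 0.3 = 1.20. For ≤ 6 weeks, d = 3.69 × ln 1.20 = 0.67, and the rejection probability is 10.3%.

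The same formula applies to objective 1. At observed HRs of 1.05, 1.20 and 1.40 the rejection probability for breastfeeding is 5.5%, 12.4% and 30.7%.

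**Step 4. The other direction.** If these cases are unrelated to exposure (HR_E = 1) and HR_P = 1, the error rate stays at 5%. If HR_P = 2.0 and HR_E = 1, the breastfeeding HR is diluted to 1.98 (q = 2%) or 1.80 (q = 20%), and power falls from 85% to 84% or 72%.

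The calculation assumes proportional hazards in both components and the planned event totals. It ignores any loss of precision from overlap weighting.

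**The case against.** The case for leaving the text alone has four parts.

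- **Wording.** The description says what perforation may be, which need not be exhaustive. The same-date rule applies only if perforation has occurred, so the parenthesis may merely illustrate overlap. This is a possible reading, but the vagina is not the uterus, and the text does not say whether the cervix counts as uterine. The ambiguity remains.
- **Operational force.** The illustration stands only in Protocol 9.3.3; Protocol 4.6.2 and SAP 3.2 state the rule without it. Outcomes come from algorithms built in the validation study, and operational definitions sit in the Data Structure Template (SAP section 4). Neither is in these documents, so the algorithms may already settle the question. This stands. It also means that the brevity of SAP 3.2 does not show the anatomical definition was abandoned.
- **Size.** A reader might infer that a timing effect on expulsion does enter the primary endpoint and yields a false positive. The documents do not support that. They do not show that such cases are numerous, that they share expulsion's risk factors, or that expulsion varies with timing, which objectives 21 to 23 leave open. The false-positive figures also need a true perforation HR of exactly 1. Protocol Table 2 reports a relative risk of 2.3 (1.1-4.7) for delivery within 36 weeks among women not breastfeeding. With HR_P = 2.3, q = 10% and HR_E = 3 to 4, the mixture gives 2.07 + 0.30 to 0.40 = 2.37 to 2.47, a modest shift in size and not a false positive.
- **Ban on analyses.** A reader might infer that the SAP forbids any look at these cases. It bars a composite outcome and a subgroup analysis of women with both outcomes. Counting them by exposure, or recoding them in a sensitivity run, is neither.

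Ordinary expulsions are also untouched; only same-date dual cases are at issue.

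**Conclusion.** The two parts of Protocol 9.3.3 do not agree on which sites make a primary event, and SAP 3.2 does not resolve it. As written, vaginal or cervical cases can count as uterine perforation and can carry an exposure effect on expulsion into objectives 1 and 2, and no planned table would show how many there are.

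The consequence cannot be sized from the documents. It runs from negligible (share 2-5%, expulsion HR near 2, observed HR 1.02-1.05) to serious (share 10-20%, expulsion HR 3-4, observed HR 1.2-1.6 and false rejection of 10-41% for ≤ 6 weeks or 23-89% for > 6 to ≤ 14 weeks). Both ends rest on assumed inputs and on a true perforation HR of 1. The unknown share is itself the reason to report the count. This should be corrected before analysis; it does not invalidate the design.

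**What to change.** 1. Reconcile the two sentences of Protocol 9.3.3 with the definition that the validated algorithms actually apply, and list the qualifying sites in SAP 3.2. The documents do not show which definition was intended, so the algorithms should decide.
2. Add a table of same-date dual-classified cases by breastfeeding status and postpartum category, pooled and by site where counts allow.
3. Add one sensitivity rerun of objectives 1 and 2 in which these cases are not counted as perforation: vagina- or cervix-only cases where location can be extracted, otherwise all same-date dual cases. Keep the primary analysis as planned.

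The sentence on composite and subgroup analyses can stay.

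Cost: wording changes, one small table and one rerun. The all-dual-cases version needs only the two outcome dates, which SAP 3.2 already defines as separate variables. The downside is that genuine perforations that also expelled on the same date drop out of that sensitivity analysis. Their number is unknown, which is why the count in item 2 should be shown beside it.
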